# 1 SYNOPSIS

Title of Study	A Phase 3, Multicenter, Open-Label Study to Assess the Long-Term Safety of REL-1017 as a Treatment of Major Depressive Disorder (RELIANCE-OLS)
Sponsor	Relmada Therapeutics, Inc. (Relmada)
Investigators/Study Sites	Approximately [REDACTED] planned in the United States
Phase of Development	3

Objectives	Endpoints
Primary	
To evaluate the long-term safety and tolerability of REL-1017 as adjunctive treatment to an approved antidepressant therapy (ADT) and as a monotherapy.	
 
• Treatment-emergent adverse events (TEAEs)
 

Secondary	
To evaluate the long-term safety of REL-1017 as adjunctive treatment to an approved ADT and as a monotherapy.	
 
• Evaluate the effects on the electrocardiogram (ECG), including heart rate, pulse rate (PR), QRS, and QT interval with Fridericia's correction (QTcF) intervals
 
• Vital signs and weight
 
• Physical examination
 
• Clinical laboratory parameters (chemistry, hematology, and urinalysis)
 
• Columbia-Suicide Severity Rating Scale (C-SSRS)
 
• Clinician-Administered Dissociative States Scale (CADSS)
 
• [REDACTED]
 

Exploratory	
To evaluate the impact and long-term durability of REL-1017 as an adjunctive treatment to an approved ADT and as a monotherapy over a 1-year period on depression, [REDACTED] [REDACTED] [REDACTED] [REDACTED]	
 
• The Montgomery-Åsberg Depression scale (MADRS10) 
 
○ Absolute value and change from Baseline of MADRS10 total score
 
○ Remission rate (total score <math>\leq 10</math>)
 
○ Response rate (improvement <math>\geq 50\%</math> compared with total Baseline score)
 
○ Time course of changes from Baseline
 
 
 
• Clinical Global Impression of Severity (CGI-S) score
 
• Hamilton Anxiety Rating Scale (HAM-A) total score
 
• Symptoms of Depression Questionnaire (SDQ) total score
 
• Sheehan Disability Scale (SDS) domain score
 
• Clinical Global Impression of Improvement (CGI-I) score
 
• [REDACTED]
 
• [REDACTED]
 
• [REDACTED]
 
• [REDACTED]
 

- A double-barrier protection method (e.g., condom, sponge, or vaginal diaphragm with spermicide cream, foam, or gel)
- Abstinence from heterosexual intercourse is accepted if this is the participant's usual lifestyle and must be continued until at least 2 months after the last dose of study drug.

Women who are not of childbearing potential must be congenitally or surgically sterile (hysterectomy and/or bilateral oophorectomy/salpingo-oophorectomy, as determined by the participant's medical history) or must be post-menopausal. Post-menopausal is defined as being amenorrheic for at least 1 year without another cause and a follicle-stimulating hormone (FSH) level  $\geq 40$  mIU/mL as confirmation.

6. Diagnosed with MDD as defined by the Diagnostic and Statistical Manual, Fifth Edition (DSM-5), and confirmed by the Structured Clinical Interview for DSM-5 Disorders (SCID-5).
7. Hamilton Depression Rating Scale-17 (HAM-D17) [REDACTED] at Screening and independently confirmed by State versus trait; Assessability; Face validity; Ecological validity; and Rule of three Ps [pervasive, persistent, and pathological] (SAFER) assessment.
8. At Baseline, before definitive admission and randomization of the participant, the MADRS10 scale will be administered and the participant must show a MADRS10 [REDACTED]
9. Diagnosed with a current major depressive episode (MDE) lasting from 8 weeks to 36 months as defined by the DSM-5 and confirmed by the SCID-5 for MDD, as well as independent confirmation of the HAM-D17 score, [REDACTED]

[REDACTED]  
[REDACTED]  
[REDACTED]  
[REDACTED]

For *de novo* participants enrolling for REL-1017 adjunctive therapy:

10. Treated for at least 6 weeks prior to Screening and stabilized for at least 6 weeks prior to Baseline on an approved dosing regimen of ADT medications (e.g., selective serotonin reuptake inhibitor [SSRI], serotonin and norepinephrine reuptake inhibitor [SNRI], bupropion (a norepinephrine–dopamine reuptake inhibitor [NDRI] and nicotinic receptor antagonist) during the current MDE, and committed to remaining on the same stable dosing regimen during the Screening period and for the entire study duration, [REDACTED]

[REDACTED]  
[REDACTED]  
[REDACTED]  
[REDACTED]

Note: Discontinuation of any of the listed ADT must occur at

	
least 6 weeks prior to Baseline.
 
[REDACTED]
 
[REDACTED]
 
Note: An electronic dosing diary (eDiary) will be used beginning at Screening to document the stability of background antidepressant(s); only participants reporting a minimum of 80% adherence during Screening will be randomized.
 
11. [REDACTED]
 
[REDACTED]
 
[REDACTED]
 
[REDACTED]
 
[REDACTED]
 
[REDACTED]
 
[REDACTED]
 
For de novo participants enrolling for REL-1017 monotherapy:
 
12. [REDACTED]
 
[REDACTED]
 
[REDACTED]
 
[REDACTED]
 
[REDACTED]

Exclusion Criteria (de novo participants only)
	
REL-1017-310 de novo participants will undergo Screening assessments. Individuals meeting any of the following criteria are ineligible to participate in this study.
 
 
1. History or presence of clinically significant abnormality as assessed by physical examination, medical history, 12-lead ECG, vital signs, or laboratory values, which in the opinion of the Investigator, Medical Monitor, or Sponsor designee would jeopardize the safety of the participant or the validity of the study results, including established QT prolongation, long QT syndrome, torsades de pointes, bradyarrhythmia, ventricular tachycardia, uncompensated heart failure (greater than New York Heart Association [NYHA] Class 1 congestive heart failure [CHF]), uncontrolled hypokalemia, or uncontrolled hypomagnesemia.
 
2. More than class 2 angina pectoris or a myocardial infarction (MI) or acute coronary syndrome within the past 3 months.
 
3. Any medical, psychiatric condition, or social context that, in the opinion of the Investigator, Medical Monitor, or Sponsor designee is likely to unfavorably alter the risk-benefit of subject participation, to interfere with protocol compliance, or to confound safety or efficacy assessments.
 
4. Have any significant illness, of any nature, including possible severe acute respiratory syndrome coronavirus 2 (SARS-CoV-2) related fever or other symptoms, requiring hospitalization,
 

emergency treatment, or isolation (quarantine) within 4 weeks prior to Screening or during the Screening period, and as determined by the Investigator.

5. History or first degree relative with history of unexplained sudden death or long QT syndrome.
6. Triplicate 12-lead ECG with average QTcF  $\geq$ 450 msec, and/or a QRS interval  $\geq$ 120 msec at Screening.
7. Current or recent uncontrolled orthostasis or orthostatic hypotension necessitating treatment.
8. Poorly controlled diabetes as defined by a glycosylated hemoglobin (HbA1c)  $>$ 7.5%, despite standard care.

9. [REDACTED]

10. [REDACTED]

12. [REDACTED]

13. [REDACTED]

15. History of allergy or hypersensitivity to methadone or related drugs.

16. [REDACTED]

17. Participants who, in the Investigator's judgment, are at significant risk for suicide. A participant with a C-SSRS ideation score of 4 or 5 within the last 6 months or any suicide attempt within the past year of either Screening or Baseline must be excluded.

18. Any lifetime history of bipolar I or II disorder, psychosis and/or mania as defined by the DSM-5 and confirmed by psychiatric history and/or examination by the Investigator.

19. Comorbid moderate to heavy alcohol or substance use disorder, as defined by DSM-5, at Screening or within the 12 months prior to Screening. Heavy drinking is defined as an average of 3 or more drinks per day, in the last month.

20. A positive result on the urine drug/alcohol screen within 30 days prior to Baseline (Day 1). At Investigator discretion, in consultation with the Medical Monitor, a retest is permitted.

21. [REDACTED]


Statistical Data Analysis
	
Study analysis populations, defined as follows:
 
Screened/Enrolled Set: The Screened/Enrolled Set will include all participants who signed an informed consent.
 
Full Analysis Set (FAS): All participants who received at least 1 dose of study drug in the OLS and had at least 1 post-Baseline efficacy assessment, irrespective of any deviation from the protocol or premature discontinuation. The FAS will be used for analysis of efficacy.
 
Safety Set: All participants who received at least 1 dose of study drug in the OLS. This population will be used for the analysis of safety.
 
Safety data analysis
 
Descriptive statistics of the safety and efficacy of the participants in the OLS will be presented based on the prior double-blind treatment groups: Double-blind placebo, double-blind REL-1017, de novo. In general, the Baseline for each assessment will be the last value collected prior to the first open-label dose.
 
Summaries of efficacy results will be presented for the FAS, and summaries of safety results will be presented for the Safety Set; all will be summarized by the treatment groups “REL-1017 in double-blind study,” “placebo in double-blind study,” “de novo,” “pooled placebo and de novo,” and “overall”.
 
Continuous safety and tolerability assessments (e.g., vital signs, weight, BMI, body temperature, ECG parameters, and laboratory parameters) will be summarized using descriptive statistics for values for each visit, and additionally for change from Baseline of OLS.
 
The time course of absolute values and change from Baseline will be presented in descriptive statistics and figures.
 
Categorical safety data (e.g., categorical laboratory parameters, ECG overall evaluation, QT/QTcF categories) and central tendency effects will be presented by number and percentage of participants in the respective category for each visit.
 
The number and percentage of participants with TEAEs, serious adverse events (SAEs), AEs associated with discontinuation, and TEAEs by severity and relationship to study treatment will be summarized by system

---	---

	
organ class and preferred term, using the Common Terminology Criteria for Adverse Events (CTCAE) v5.0.
 
All summaries of TEAEs will be provided for the TEAEs in OLS (i.e., AEs that started or worsened in severity after first dose in the OLS).
 
Comorbidities and comedications will be summarized in count and frequency tables.
 
Exploratory Efficacy variables
 
Continuous efficacy variables will be reported using descriptive statistics for values for each visit, and additionally for change from Baseline of OLS. The time course of absolute values and change from Baseline will be presented in figures.
 
Categorical efficacy data will be presented by number and percentage of participants in the respective category for each visit.

--	--

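### For participants from double-blind REL-1017, and in the overall column, MADRS10 response counted from open-label entry cannot show maintained benefit

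*Combined protocol and SAP*

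**What the plan says.** Only the synopsis (section 1) of the combined protocol and SAP was supplied.

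- **Objective.** The exploratory objective begins "To evaluate the impact and long-term durability of REL-1017" and covers depression over 1 year.
- **Endpoints.** The MADRS10 endpoints are the absolute score and its change, remission (total score of 10 or less), response, and time course. Response is an improvement of at least 50% "compared with total Baseline score". That line does not say which Baseline is meant.
- **Baseline.** The only definition is under Statistical Data Analysis, Safety data analysis: "In general, the Baseline for each assessment will be the last value collected prior to the first open-label dose". Despite the heading, the sentence just before it covers both safety and efficacy.
- **Efficacy summaries.** Under Exploratory Efficacy variables, continuous measures are given as values by visit and as change from the OLS (open-label study) Baseline. Categorical measures are counts and percentages by visit, with no baseline of their own.
- **Columns.** Under Safety data analysis, "all will be summarized by the treatment groups": prior REL-1017, prior placebo, de novo, prior placebo pooled with de novo, and overall.
- **Entry.** Inclusion criterion 8 reads "At Baseline, before definitive admission and randomization of the participant, the MADRS10 scale will be administered and the participant must show a MADRS10", followed by a redacted cut-off.

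**The concern.** Participants from double-blind REL-1017 have been on the drug before OLS entry, so they bear most directly on whether its benefit lasts. If their reference score is taken after that benefit has been gained, keeping it registers as no improvement. The response rate then measures further improvement after entry. It places a participant who holds and one who relapses in the same category.

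The overall column adds a second difficulty. It combines further improvement in people already treated with REL-1017 and response in people who start it at OLS entry. A reader who took that percentage as evidence on durability would be reading two different quantities as one.

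**Working it through.** The synopsis gives no response rate or sample size on this point, so there is no figure to reproduce. The check applies its own definitions.

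**Inputs from the synopsis.** Response is at least 50% improvement on Baseline; remission is a total score of 10 or less; Baseline is the last value before the first open-label dose.

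**Inputs assumed.** The double-blind baseline scores *B* and OLS entry scores *E* below are illustrations. MADRS10 totals are treated as integers.

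**1. Holding the entry score.** Improvement = (E − score)/E. If score = E, this is 0% for every E, so the participant is a non-responder at every visit.

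**2. Improvement required from the double-blind baseline.** A participant entering with improvement *r* must halve the remaining score, so the requirement is 1 − (1 − r)/2.
- r = 0.50: 1 − 0.25 = 75%.
- r = 0.65: 1 − 0.175 = 82.5%.

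**3. Order of the two cut-offs.** Response needs a score of at most floor(E/2); remission needs at most 10.
- floor(21/2) = 10 and floor(22/2) = 11, so for E from 1 to 21 response implies remission.
- For E from 11 to 19, floor(E/2) is 5 to 9, so response is the harder target. From 12 it needs 6 or less (6 points further), while remission needs 10 or less (2 points).
- A responder from B enters at floor(B/2) or below, which is at most 21 for every B up to 43.

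**4. One participant, B = 34, E = 12.** Improvement at entry is (34 − 12)/34 = 64.7%.

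| Course in the OLS | From OLS Baseline | From double-blind baseline | Remission |
|---|---|---|---|
| Holds at 12 | 0%: non-response | 64.7%: response | No |
| Relapses to 30 | (12 − 30)/12 = −150%: non-response | (34 − 30)/34 = 11.8%: non-response | No |
| Falls to 6 | 50%: response | 28/34 = 82.4%: response | Yes |

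As a response category, only the double-blind baseline separates the first two rows.

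**5. Width of the gap.** Held scores that are a response from B but neither response nor remission in the OLS run from 11 to floor(B/2).

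| Assumed B | Held scores in the gap | Integer scores |
|---|---|---|
| 24 | 11–12 | 2 |
| 30 | 11–15 | 5 |
| 34 | 11–17 | 7 |
| 40 | 11–20 | 10 |

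**6. Direction at group level.** Let *s* be the share of prior REL-1017 participants who enter at least 50% improved and hold. Let *p* be the response rate in the rest, taken as equal under both baselines. The rate is (1 − s)p from OLS Baseline and s + (1 − s)p from the double-blind baseline. With assumed p = 0.4:

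| s | OLS Baseline | Double-blind baseline |
|---|---|---|
| 0.2 | 32% | 52% |
| 0.4 | 24% | 64% |
| 0.6 | 16% | 76% |

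The two rates move in opposite directions. These percentages show direction only; the documents give neither s nor p.

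**The case against.** **Other outputs bear on durability.** Absolute MADRS10 and its change by visit, time-course figures, remission and CGI-S are all planned by prior treatment group. Holding at 12 and relapsing to 30 differ as a change of 0 against +18 and as absolute scores of 12 against 30. A participant who enters at 10 or less and holds counts as a remitter throughout. This stands, and it limits the point to one gap: no categorical MADRS10 measure shows whether a non-remitting response was kept.

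**Only a redacted synopsis is visible.** The Baseline sentence is hedged, the response line names no Baseline, and a fuller section might define another. This also stands and limits confidence. The supplied text states no exception, though, and if one is intended the synopsis should say so.

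**Stronger readings that the documents do not support.**
- A reader might infer that the response rate is uninformative on durability for everyone. For de novo participants, who have their own column, OLS Baseline precedes REL-1017, so response by visit over 1 year does bear on durability.
- A reader might extend the point to prior-placebo participants. The arithmetic is the same for any who enter improved, but improvement gained on placebo is not a REL-1017 effect. OLS Baseline is their proper pre-drug value.
- A reader might carry the point to safety, where continuous assessments "will be summarized using descriptive statistics for values for each visit, and additionally for change from Baseline of OLS". An ECG, weight or laboratory effect already present at entry would be missing from the change in prior REL-1017 participants. That is a separate question: the documents do not indicate whether any such effect exists, and absolute values and QT/QTcF categories by visit are planned. It forms no part of this point.

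**Conclusion.** The point holds for participants from double-blind REL-1017 and for the overall column. On the natural reading, their MADRS10 response rate measures further improvement after entry and cannot show that earlier benefit was maintained.

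The threshold arithmetic is exact. The number of participants affected is unknown, because the documents do not say how many enter improved or at what scores.

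The verdict rests on two assumptions:
- The general Baseline rule applies to response.
- Inclusion criterion 8 does not bind rollover participants. The supplied text does not say, although the exclusion criteria are marked as applying to de novo participants only. If criterion 8 does bind them, the point covers only those who enter improved and still meet its redacted cut-off.

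Severity is minor: this is one exploratory endpoint, summarised descriptively, and the primary endpoint (TEAEs) is untouched.

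**What to change.** 1. Keep OLS Baseline for the existing change and response tables, state in the SAP that response uses it, and label the baseline in each table.
2. For prior REL-1017 participants, add descriptive MADRS10 change and response from the pre-randomization double-blind baseline.
3. For the same group, add maintenance of response by visit. Among those at least 50% below the double-blind baseline at OLS entry, give the number and percentage still at least 50% below it. Show discontinued or missing participants as their own row.
4. State that the overall response rate is not to be read as evidence of durability.

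The cost is SAP wording, a merge of parent-study baselines (assumed available and compatible, since the parent protocols were not supplied) and one extra table. No existing table is replaced and no new data are collected. Responders at entry are a subgroup formed after randomization, so the maintenance table supports description only, not a comparison.

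### The objectives cover REL-1017 both as adjunctive treatment and as monotherapy, but none of the five reporting groups in the synopsis is defined by regimen, so no stated column identifies a monotherapy result

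*Combined protocol and SAP*

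**What the plan says.** The Objectives and Endpoints table of the Synopsis (Section 1) names both uses at every level:

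- Primary: "To evaluate the long-term safety and tolerability of REL-1017 as adjunctive treatment to an approved antidepressant therapy (ADT) and as a monotherapy".
- Secondary: "To evaluate the long-term safety of REL-1017 as adjunctive treatment to an approved ADT and as a monotherapy".
- Exploratory: "To evaluate the impact and long-term durability of REL-1017 as an adjunctive treatment to an approved ADT and as a monotherapy".

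The inclusion criteria carry the same division into enrolment. One block applies to de novo "participants enrolling for REL-1017 adjunctive therapy" and requires them to be "stabilized for at least 6 weeks prior to Baseline on an approved dosing regimen of ADT medications". A separate block applies to de novo "participants enrolling for REL-1017 monotherapy"; its content is redacted.

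The Statistical Data Analysis row gives the grouping twice under Safety data analysis. First, descriptive statistics "will be presented based on the prior double-blind treatment groups: Double-blind placebo, double-blind REL-1017", with de novo as the third group. Then, for efficacy on the FAS and safety on the Safety Set, "all will be summarized by the treatment groups “REL-1017 in double-blind study,” “placebo in double-blind study", followed by de novo, a pool of prior placebo and de novo, and an overall group. The list shows no sign of redaction. The same row says that comorbidities and comedications will be tabulated as counts and frequencies.

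**The concern.** The grouping follows a participant's history (prior arm, or no prior study), whereas the objectives are framed by how REL-1017 is used now (with an antidepressant, or alone). These are different classifications, and the first does not recover the second.

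If tables are built to the synopsis as written, a reader who wants the adverse-event or QTcF profile of REL-1017 given alone has no stated column to consult. A pattern confined to one use could be diluted in a column that combines both. ECG effects, including QTcF, are a secondary endpoint, so this reaches beyond the TEAE tables.

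The concern is about identifying results for each use. It is not that pre-existing antidepressant effects are left uncontrolled, since other provisions deal with part of that.

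**Working it through.** The synopsis states no sample size, event rate or regimen split on this point, so the check compares the texts.

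**Step 1: objectives.** Primary, secondary and exploratory each name adjunctive use and monotherapy: 3 of 3.

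**Step 2: entry.** De novo participants can enter under either use, through separately headed criteria. Any group that contains de novo participants can therefore contain both regimens.

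**Step 3: reporting groups.**

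| Reporting group | Defined by | Defined by regimen? | Regimen content |
|---|---|---|---|
| Prior REL-1017 | Prior double-blind arm | No | Not stated |
| Prior placebo | Prior double-blind arm | No | Not stated |
| De novo | No prior study | No | Can mix |
| Prior placebo + de novo | Pool | No | Can mix |
| Overall | Everyone | No | Can mix |

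Groups defined by regimen: 0 of 5. Groups that can mix regimens: 3 of 5. Groups with regimen unstated: 2 of 5 (0 + 3 + 2 = 5).

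**Step 4: other displays.** The rest of the Statistical Data Analysis row was read for a subgroup, stratum or extra column by regimen, and it names none. The comedication table is the only display where background antidepressant use could appear. It is a frequency table and is not linked to TEAEs, ECG or efficacy.

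**Step 5: what is already handled.** Three provisions limit the influence of antidepressant effects that predate REL-1017:

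- adjunctive de novo participants must have been stable on their antidepressant for at least 6 weeks before Baseline;
- Baseline is in general the last value before the first open-label dose;
- TEAEs count only events that begin or worsen after that dose.

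These provisions bear on attribution. None of them separates the results of the two uses.

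**The case against.** The strongest reply is that this reads too much into a synopsis. Subgroup displays usually sit in the statistics section of the protocol body or in the SAP, and only the synopsis was available here. Listing five groups does not say that no other display will be made. This stands as a limit on scope: a by-regimen display elsewhere cannot be ruled out. It does not remove the point. The synopsis does not merely omit detail; it gives a reporting rule that applies to all summaries, and that rule does not match the objectives beside it.

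A second reply is that the objective may simply describe the population covered, without promising a separate result for each use, so that overall tables would answer it. That reading is possible. However, the two uses are named in every objective and have separate entry criteria, so a reader will reasonably expect to see each one.

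A third is that the consequence is unproven. The rollover groups may be single-regimen, the monotherapy group may be small, all analyses are descriptive, and regimen is not described as randomised. All of this is accepted. It rules out a claim of bias or of a numerical effect, and it means that a split would not settle attribution. It does not argue against showing how many participants were on each regimen and what happened to them. Deriving the split afterwards is possible, but the choice would then be made with results in hand.

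Finally, the monotherapy criterion is redacted, so the visible text does not show that regimen at entry stays fixed throughout exposure. This stands, and it is why the display should be labelled by regimen at entry.

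**Conclusion.** The concern holds for the synopsis text. All 3 objectives name both uses, 0 of 5 reporting groups is defined by regimen, 3 of 5 can mix regimens, and the regimen of the other 2 is not stated. No stated column identifies a monotherapy result for TEAEs, QTcF or efficacy.

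These counts describe the reporting structure and do not measure an effect. How far a mixed column could mask a regimen-specific pattern, and how precise a monotherapy column would be, cannot be calculated without the numbers in each regimen and the event rates.

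The conclusion rests on two conditions: that the five-group rule is applied as the synopsis words it, and that no display by regimen is specified in parts of the plan not available here. If one is, the remaining defect is a missing cross-reference. Otherwise this should be fixed before the table shells are finalised, because a distinction in the primary objective has no matching output.

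**What to change.** First check whether the protocol body or SAP already specifies displays by regimen. If so, add a cross-reference in the synopsis. If not:

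- Prespecify regimen at entry to the open-label study (adjunctive or monotherapy) as a display factor.
- Present the number of participants, TEAEs, SAEs, AEs associated with discontinuation, and ECG/QTcF summaries by regimen, at least within de novo and overall.
- Do the same within the prior-arm groups if both regimens occur there. If a prior-arm group is single-regimen, say so in the table heading.
- State that these displays are descriptive and that differences between regimens are not randomised comparisons.

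The cost is SAP wording and a limited set of additional tables, with no extra visits, participants or procedures. For de novo participants, regimen at entry follows from the set of criteria they enrolled under. For rollover participants it would have to come from the parent study or from the comedication data already planned for summary. The drawbacks are a longer table package and some small cells.

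### The synopsis sets QT/QTcF and laboratory categories out by visit and names no worst post-Baseline summary, so its tables only bound how many participants ever crossed a threshold

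*Combined protocol and SAP*

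**What the plan says.** All of this is in Section 1, Synopsis.

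- **Endpoints.** The secondary safety endpoints include "Evaluate the effects on the electrocardiogram (ECG), including heart rate, pulse rate (PR), QRS, and QT interval with Fridericia's correction (QTcF) intervals" and "Clinical laboratory parameters (chemistry, hematology, and urinalysis". The exploratory objective refers to treatment "as a monotherapy over a 1-year period".
- **Categorical safety data.** One rule covers several kinds of data: "Categorical safety data (e.g., categorical laboratory parameters, ECG overall evaluation, QT/QTcF categories" are listed together, and the sentence ends with "QT/QTcF categories) and central tendency effects will be presented by number and percentage of participants in the respective category for each visit".
- **Continuous ECG and laboratory data.** These are summarized at each visit and as change from OLS Baseline, with time-course statistics and figures. No maximum or worst value per participant is named.
- **Baseline.** In general, "the Baseline for each assessment will be the last value collected prior to the first open-label dose".
- **Adverse events.** Here the unit is the participant over the whole open-label period: "The number and percentage of participants with TEAEs, serious adverse events (SAEs), AEs associated with discontinuation" are to be summarized, with TEAEs defined as "AEs that started or worsened in severity after first dose in the OLS".

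The supplied synopsis mentions no worst post-Baseline, any-time or shift summary for ECG or laboratory categories. The statistical analysis rows carry no redaction marks, so visible blacking-out does not explain this.

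**The concern.** A reader of a long-term safety study wants to know what share of participants ever had a notable QTcF or laboratory value on treatment. A by-visit table answers a different question: what share were in the category on a given occasion. If different people cross at different visits and then return to range, every row of the table stays small while the number ever affected grows.

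The adverse event tables do not close the gap. They count participants over the whole period, but they capture a crossing only if it was reported as an adverse event, and they do not give the proportion in each QTcF or laboratory category.

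For categories defined by an absolute value, a by-visit count also mixes new crossings with values that were already in the category at Baseline. This does not apply to categories defined by change from Baseline. The supplied text does not say which kind is meant.

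**Working it through.** The supplied text gives no figure to reproduce: it has no ECG or laboratory visit count, sample size, category cut-off, event rate or measurement SD. The bound below is general. Every number put into it is an assumption.

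**Bound.** Let n_v be the number in the category at visit v, N the number of participants, and E the number in the category at one or more tabulated visits.

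- Everyone counted at visit v is in E, so E ≥ max(n_v).
- Everyone in E is counted at least once, so E ≤ sum(n_v), and E cannot exceed N.
- Hence max(n_v) ≤ E ≤ min(N, sum(n_v)).

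Full enumeration of a small case (4 participants, 3 visits, 1 crossing per visit) gives E = 1, 2 and 3, so every value in the range can occur. A crossing seen only at an assessment outside the tabulated visits would not be covered by this bound at all.

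**Illustration with counts.** For by-visit counts 1, 2, 0, 3, 1, 2:

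- lower limit: max = 3
- upper limit: 1 + 2 + 0 + 3 + 1 + 2 = 9

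The same table fits anything from 3 to 9 participants.

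**Illustration with percentages.** With a constant denominator and proportion p at each of K visits, the ever-proportion lies between p and min(1, K × p).

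| p per visit | K = 4 | K = 6 | K = 12 |
|---|---|---|---|
| 1% | 1–4% | 1–6% | 1–12% |
| 2% | 2–8% | 2–12% | 2–24% |

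The lower end applies if the same people cross each time, and the upper end if different people do. If crossings were independent between visits, 2% at each of 6 visits would give 1 − 0.98^6 = 11.4%, close to the upper end.

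**Noise in the ever-crossed figure.** Assume no drug effect, independent normal error with the same SD at Baseline and at each of K ECGs, and a category defined as a QTcF increase above 30 msec. The proportion ever in the category is

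1 − ∫ φ(z) Φ((30 + SD·z)/SD)^K dz.

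For K = 1 this is the upper normal tail at 30/(SD·√2). With SD 8 that is 30/11.31 = 2.65, which gives 0.40%.

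| SD (msec) | K = 1 | K = 4 | K = 6 | K = 12 |
|---|---|---|---|---|
| 6 | 0.02% | 0.08% | 0.11% | 0.21% |
| 8 | 0.40% | 1.41% | 1.99% | 3.42% |
| 10 | 1.69% | 5.47% | 7.39% | 11.71% |

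With SD 8 and K = 3 the figure is 1.10%. A worst-value percentage therefore rises with the number of ECGs even when the drug does nothing, and it has to be read beside the number of assessments.

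**The case against.** The strongest reply is that this is a synopsis. It need not list every table, its examples are introduced as examples, and no fuller statistical section was supplied. Reporting is descriptive, no test or decision rule in the supplied text depends on it, and the tables could be produced later from participant-level data. Abnormalities reported as adverse events are already counted per participant.

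Much of this stands, and it limits the point. It does not remove it: the synopsis does state a summary level for these data, and followed as written that rule cannot give the proportion ever affected.

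A reader might infer more than the documents support:

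- **That by-visit tables are the only planned output.** The sentence does not say so, and a fuller section may already specify the worst-value tables.
- **That roll-over participants had no QTcF entry limit, so the groups start from different categories.** The Screening limit does sit in a list for de novo participants. But much of the eligibility text is redacted or absent from what was supplied, so silence about roll-over participants shows nothing.
- **That by-visit counts never separate new from pre-existing values.** This fails for change-from-Baseline categories.
- **That the illustrative ranges estimate this trial.** They rest wholly on assumed inputs, and the upper ends need different people to cross at every visit.

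**Conclusion.** The point holds in a limited form. In the supplied synopsis, laboratory and QT/QTcF categories are to be shown visit by visit, and no worst post-Baseline summary is named. Such tables fix the number who ever crossed a threshold only to an interval and can understate it, on endpoints that the study names as secondary safety endpoints.

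The bound needs no assumption about the data beyond counting over tabulated visits. Its width here is unknown. It is zero if the same people cross each time, and it could be several-fold if crossings are scattered. The consequence is confined to descriptive safety reporting. The change is worth making, with medium confidence, because a fuller section that already has these tables would leave only a wording mismatch in the synopsis.

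**What to change.** Keep the by-visit tables. Unless a fuller statistical section already does so, add for the Safety Set, by the planned summary groups:

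- number and percentage of participants by worst post-Baseline QTcF category, both absolute and change from OLS Baseline
- number and percentage by worst post-Baseline laboratory category
- Baseline-to-worst shift tables for both
- a statement that scheduled, unscheduled and early-termination assessments all count
- the number of assessments or length of follow-up per group beside these percentages

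If a fuller section already contains these tables, align the synopsis sentence with it.

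The cost is a few tables from data already collected. The new percentages will look less favourable than the by-visit ones and will grow with the number of assessments through measurement noise, so they complement the by-visit tables and do not replace them. Setting the summary level in advance also avoids choosing it after the open-label data have been seen.
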